## **Abstract**

### **Background**

Despite current resuscitation strategies, circulatory shock and organ injury after cardiac surgery occur in 25-40% of patients. Goal-directed resuscitation after cardiac surgery has generated significant interest, but clinical practice to normalize hemodynamic variables including mean arterial pressure, cardiac filling pressures, and cardiac output may not reverse microcirculation abnormalities and do not address cellular dysoxia. Recent advances in technology have made it possible to measure critical components of oxygen delivery and oxygen utilization systems in live human tissues and blood cells. The MicroRESUS study will be the first study to measure microcirculatory and mitochondrial function in patients with circulatory shock and link these findings with clinical outcomes.

### **Methods and analysis**

This will be a prospective, observational study that includes patients undergoing elective cardiovascular surgery with cardiopulmonary bypass (CPB). Microcirculation will be quantified with sublingual incident dark field videomicroscopy. Mitochondrial respiration will be measured by performing a substrate-uncoupler-inhibitor titration protocol with high resolution respirometry on peripheral blood mononuclear cells at baseline and serial timepoints during resuscitation and at recovery as a possible liquid biomarker. Plasma samples will be preserved for future analysis to examine endothelial injury and other mechanisms of microcirculatory dysfunction. Thirty-day ventilator and vasopressor-free days (VVFDs) will be measured as a primary outcome, along with sequential organ failure assessment scores, and other clinical parameters to determine if changes in microcirculation and mitochondrial respiration are more strongly associated with clinical outcomes compared to traditional resuscitation targets.

This will be the first prospective study to examine both microcirculatory and mitochondrial function in human patients with circulatory shock undergoing cardiac bypass and address a key mechanistic knowledge gap in the cardiovascular literature. The results of this study will direct future research efforts and therapeutic development for patients with shock.

## Introduction

Despite current resuscitation practices, circulatory shock and perioperative organ injury after cardiac surgery occur in 25-40% of patients [1,2]. Traditionally, causes of shock after cardiovascular surgery with cardiopulmonary bypass are classified by macrocirculatory derangements (e.g. low cardiac output, vasoplegia, hypovolemia) [3]. Interventions to normalize hemodynamic variables, including mean arterial pressure, cardiac filling pressures, and cardiac output restore the large vessel (macrocirculatory) pressure and flow targets but may not reverse underrecognized disruptions in microcirculatory blood flow and oxygen utilization. Current methods to estimate the balance of oxygen delivery ( $DO_2$ ) relative to demand ( $VO_2$ ) include blood gas-derived calculations and the measurement of downstream biomarkers of anaerobic metabolism such as blood lactate. Using these methods, previous literature has concluded that lactic acidosis after cardiac surgery is unlikely related to inadequate oxygen delivery [4]. Unfortunately these inferences fail to consider the presence of regional blood flow derangements caused by pathologic microcirculatory heterogeneity, which are also associated with severity of postoperative lactic acidosis and organ injury [5,6]. To resolve this important clinical discrepancy, a deeper understanding of the determinants of oxygen transport pathways and oxygen utilization during health, shock, and resuscitation are needed.

The microcirculation is composed of a network of vessels including arterioles, capillaries, and venules  $<100\text{ }\mu\text{m}$  in diameter where red blood cells (RBCs), leukocytes, and plasma components interface with the vascular endothelium to allow metabolic substrate exchange. Changes in microcirculatory blood flow can be caused by inflammatory-mediated vascular endothelial injury, microthrombosis, or an inadequate balance between vasoconstrictive and vasodilating agents leading to a global or heterogeneous reduction in capillary blood flow [7,8]. Incident dark field (IDF) videomicroscopy is a novel, handheld method that can directly image the human microcirculation in real time. Current generation IDF videomicroscopy has improved imaging resolution compared to previous generation devices, and can detect up to 30% more capillaries compared to side stream imaging [9,10]. As a result, important determinants of tissue oxygenation, such as microcirculatory diffusive and convective properties, can now be more accurately quantified.

Blood gas derived calculations of  $VO_2/DO_2$  balance may provide false clinical reassurance as they cannot identify microvascular injury, microvascular shunting, and other mechanisms of dysoxia which may contribute to cell injury and organ dysfunction in patients with shock [11]. Advancements in high resolution respirometry now make it possible to quantify mitochondrial respiration rapidly and reliably in live tissues [12]. Nucleated blood cells (platelets and peripheral blood mononuclear cells) are readily accessible and can be used as surrogates to study cellular respiration in acute care illnesses such as acute heart failure, hemorrhagic shock, sepsis, and patients with ischemic reperfusion injury [13–15]. It is unclear if deficiencies in oxygen delivery and utilization occur independently or concomitantly in patients with shock. Studies that simultaneously examine mitochondrial respiration and microcirculatory function, which are also tied to clinical outcomes, are vitally important to guide future research efforts in therapeutic development and perform effective interventional trials.

## Materials and methods

### Study objective

The primary objective of the MicroRESUS study is to evaluate the microcirculatory and mitochondrial function in patients following elective cardiovascular surgery with cardiopulmonary bypass, to determine if these parameters outperform traditional biomarkers and global hemodynamic measurements to predict clinical outcomes.

### Study design and setting

This is a prospective, observational, single center study with repeated measures from baseline through 30-days after surgery at the University of Pennsylvania in Philadelphia, PA, USA.

### Patient screening

Patients will be screened 24-48 hours prior to surgery using the published operative schedule. First-case elective coronary artery bypass graft (CABG) or valvular surgeries will be considered for study enrollment, pending availability of research personnel to complete the study protocol. Efforts will be made to diversify subject enrollment to accurately reflect the general cardiovascular patient population.

## **Informed consent**

Patients will be approached for consent by telephone one day prior to surgery or in person while in the preoperative area on the day of surgery. Consent will be obtained by the Principal Investigator or trained research personnel. Patient signatures will be obtained digitally via the REDcap data management system [16]. A digital copy of the consent form will be sent to the patient in addition to being retained by the study team.

## **Sample size and power**

Using data from our previous foundational work as well as unpublished pilot data, we anticipate a 1:1 allocation of patients to the high ( $PVD > 22\text{mm/mm}^2$ ) and low group ( $PVD \leq 22\text{ mm/mm}^2$ ). We will need a sample size of at least 134 subjects to detect at least a 2-day difference in ventilator and vasopressor-free days (VVFDs) with a  $\beta=0.8$ , using a one-sided t-test  $\alpha=0.05$  [5,6]. We will enroll a total of 140 subjects to allow for a 5% loss to follow-up (surgical delay, ICU delay, cancelled surgery, etc.) and exclusion due inadequate microcirculation video quality (S1 Appendix).

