#### Analysis of IDF videomicroscopy

Prior to analysis, video quality will be assessed using the 6-factor Massey quality score, which uses a semiquantitative assessment of each video for appropriate illumination, duration, focus, content, stability, and pressure. Only videos with Massey scores of <10 will be included for further analysis [17]. Three videos with the best quality score will be selected for further processing. All IDF images will be coded then analyzed using an offline, dedicated software (Automated Vascular Analysis v3.02, Microvision Medical, The Netherlands). Microvascular flow index (MFI), microcirculatory heterogeneity index (MHI), total vessel density (TVD), proportion of perfused vessels (PPV), and perfused vessel density (PWD). Individual microvessel flow will be scored as 0=no flow, 1=intermittent flow, 2=sluggish flow, or 3=continuous flow. Vessels will be considered perfused if they are scored as either sluggish or continuous flow. To ensure only vessels contributing to tissue gas exchange and metabolism are included, only vessels < 20  $\mu$ m in diameter will be analyzed. This process follows the current standard for microcirculation measurement and analysis [18]. Interobserver variation will be tested periodically in at least 10% of the subject videos to ensure minimal scoring heterogeneity between investigators.

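### 140 enrolled less the plan's own 5% loss leaves 133, one short of the stated minimum of 134, and it is unclear whether the 5% includes video-quality exclusions

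*Combined protocol and SAP*

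**What the plan says.** Under Sample size and power, the combined protocol and SAP states: "We will need a sample size of at least 134 subjects". The target is "at least a 2-day difference in ventilator and vasopressor-free days (VVFDs", tested with a one-sided t-test at α = 0.05, with an anticipated 1:1 split between high and low perfused vessel density (PVD). The power parameter is printed as β = 0.8. No SD for VVFDs is given; the section refers only to previous work and unpublished pilot data.

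Enrolment follows: "We will enroll a total of 140 subjects to allow for a 5% loss to follow-up". The reason given has two parts joined by a conjunction. The first is "5% loss to follow-up (surgical delay, ICU delay, cancelled surgery, etc"; the second, after the parenthesis closes, is "exclusion due inadequate microcirculation video quality (S1 Appendix". No separate rate is attached to the second part.

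Under Analysis of IDF videomicroscopy, the quality rule is "Only videos with Massey scores of <10 will be included for further analysis". That section gives no expected number of subjects without usable imaging.

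**The concern.** A floor, a loss rate and an enrolment figure in one paragraph should agree. Here the loss rate applied to the enrolment figure falls below the floor, and a second source of loss is named without a rate.

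The second source matters more than the first. PVD, measured from the videos, defines the two groups in the power calculation. A subject with no usable postoperative imaging cannot be placed in either group and drops out of the primary comparison, however complete the outcome data. This is also the plan's only power statement, so a reader judging a null result will rely on it.

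The symbol is a separate slip. β conventionally denotes the type II error rate, so β = 0.8 would mean 20% power. Power of 0.80 is evidently intended.

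**Working it through.** **Inputs from Sample size and power:** minimum 134 (67 per group at 1:1); enrolment 140; loss 5%; difference 2 days; one-sided α = 0.05; power read as 0.80. The SD and the video-exclusion rate are not given.

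**1. Enrolment figure**
- Usual inflation, N/(1 − d): 134/0.95 = 141.05, which rounds up to 142.
- Cruder form, N × (1 + d): 134 × 1.05 = 140.7, which rounds up to 141.
- The stated 140 is within two subjects of both results but equals neither.
- Reverse check: 140 × 0.95 = 133, and 134 − 133 = 1.
- Spare subjects: 140 − 134 = 6, and 6/140 = 4.3%.

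**2. Implied SD**

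The 134 cannot be reproduced directly without an SD, but it can be bracketed. For a one-sided two-sample t-test, power is the probability that a noncentral t variable with n₁ + n₂ − 2 degrees of freedom and noncentrality (2/SD)/√(1/n₁ + 1/n₂) exceeds the 95th percentile of the central t.
- 67 per group with power exactly 80% gives SD = 4.63 days, the largest SD for which 134 suffices.
- 66 per group with power exactly 80% gives SD = 4.60 days. At or below this, 132 would already have been enough.

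With equal groups, 134 is therefore the minimum for SDs from about 4.60 to 4.63 days.

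**3. Power at the expected evaluable number, over that SD range**

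The last two rows treat video loss as additional to the 5%. Their rates are my assumptions.

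| Situation | Evaluable of 140 | Power, SD 4.63 to 4.60 |
|---|---|---|
| Stated minimum | 134 | 80.0% to 80.5% |
| 5% total loss | 133 | 79.7% to 80.3% |
| 5%, then a further 5% for video | 140 × 0.95 × 0.95 = 126.4, about 126 | 77.8% to 78.3% |
| 5%, then a further 10% for video | 140 × 0.95 × 0.90 = 119.7, about 120 | 76.0% to 76.6% |

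Adding the losses instead of compounding them gives 140 × 0.90 = 126 and 140 × 0.85 = 119, which changes little.

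**4. The symbol**

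Power = 1 − β, so β = 0.8 gives 1 − 0.8 = 0.20. The intended statement corresponds to β = 0.20.

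**The case against.** The strongest reply is that the certain part is one subject. 140 is a round number close to 141.05, and a required N is itself rounded up, so power at 133 may still be 80% or more. This stands. A reader might infer that the enrolment figure fails to deliver the planned power; the documents do not show that. Quoting 79.7% alone would pick the pessimistic end of the range.

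A second reply is that the sentence can be read as a single allowance of about 5% covering both kinds of loss. This also stands as a possible reading. The list in the parenthesis mentions only delays and cancellation, and video quality comes after it, which favours two separate losses, but the wording does not settle it. A reader might infer that nothing has been set aside for unusable videos. That holds only on the two-loss reading. S1 Appendix, cited directly after the video clause, is not in the text available to me and may give a rate or a derivation.

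Third, the 5% and 10% video losses have no basis in the documents, and the plan limits such losses. It captures three to five clips at each imaging session, uses the best three, and excludes patients who cannot tolerate imaging. The Massey rule removes videos, not necessarily subjects. This is fair, and the larger scenarios are illustrations, not forecasts.

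Finally, the β label does not affect the enrolment arithmetic. That is correct; it belongs here only because it sits in the same paragraph and can be corrected in the same edit.

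**Conclusion.** The point holds as a minor inconsistency that is cheap to correct. As written, 140 less 5% gives 133 against a stated minimum of 134. The shortfall in the count is certain; a shortfall in power is not, since power at 133 lies between about 79.7% and 80.3%.

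The size of any real problem depends on what the 5% covers. If it includes video exclusions, only the one-subject gap remains. If it does not, no allowance remains for them, and the assumed further losses of 5% and 10% bring power to about 78% and 76%.

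These power figures assume equal or near-equal groups, the one-sided t-test as stated, β = 0.8 read as power 0.80, and an SD back-solved from 134 because the plan gives none.

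**What to change.** Keep enrolment at 140 and revise the sample-size paragraph as follows:

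- State whether the 5% includes video-quality exclusions. If it does not, give their expected rate with its source, or label it as an assumption.
- State the expected evaluable number: 133 if total loss is 5%, fewer if video loss is additional.
- Give the SD used and the power at that evaluable number, calculated from the investigators' own SD and not from the back-solved value used here.
- Replace β = 0.8 with power = 0.80 (β = 0.20).

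A possible wording: With 140 enrolled, a loss of 5% [including / excluding] subjects without usable postoperative imaging, and [x]% unusable imaging if counted separately, we expect about [N] evaluable subjects. With an SD of [s] days this gives [y]% power (one-sided α = 0.05) to detect a 2-day difference in VVFDs.

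This sentence would replace the implication that 134 is secured. Raising enrolment to 142 would close the gap on a 5% total loss, but one subject does not justify it. The cost is a sentence or two and no extra patients. The downside is that the stated evaluable number, and possibly the power, becomes slightly less favourable.

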## **Inclusion criteria**

Adult patients ( $\geq 18$  years old) receiving elective CABG or valvular surgery requiring cardiopulmonary bypass are eligible for enrollment. Post-operative patients with circulatory shock will be identified by having:

1. Either vasopressor-dependent hypotension or low cardiac output requiring inotropic support
2. Signs of end-organ injury or impaired tissue perfusion defined by one of the following criteria:
  - a. Normothermic patients with a capillary refill time  $> 3$  seconds
  - b. Serum lactate  $> 2$  mmol/dL
  - c. Mixed venous oxygen saturation ( $SvO_2$ )  $< 60\%$

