### Physiologic and pharmacologic data

Systemic hemodynamic data, perfusion data, and blood gas measurements will be collected upon ICU admission, then hourly during the first 6 hours of postoperative care. Cardiac output (CO), cardiac index (CI), central venous pressure (CVP), pulmonary artery pressure (PAP), and mixed venous oxygen saturation ( $SvO_2$ ) will be monitored continuously using a pulmonary artery catheter (Edwards Lifesciences LLC, Irvine, CA, USA). Arterial blood pressure will be measured using a standard invasive arterial line. Intraoperative and post-operative administration of blood products, intravenous fluids, vasoactive agents (vasopressor and inotropes), and sedatives will be recorded at each time point.

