#### Biological samples

Blood gas samples will be drawn into a commercial, pre-heparinized 1 mL blood sampler then immediately analyzed by an ABL90 FLEX automatic blood gas analyzer (Radiometer America Inc., Brea, California, USA). Arterial blood gas samples will be obtained by clinical staff every 1-2 hours for the first 6 hours after ICU admission based on current clinical practice. Central venous blood gas measurements will also be obtained by the study team at the time of microcirculation measurement. Hemoglobin, hematocrit, pH, PaO2, PaCO2, and glucose are also reported on each blood gas analysis. After 6 hours, blood gas analysis will be performed as needed by the clinical team. For biomarker and mitochondrial function analysis, enrolled patients will undergo phlebotomy with volumes of 15 mL drawn into K2EDTA tubes. Blood samples will then be centrifuged at room temperature using Ficoll-PaqueTM PLUS (GE) and Leucosep tubes (Greiner Bio-one). Plasma specimens will be stored at -80°C for later evaluation of the mechanisms of microcirculatory dysfunction. Peripheral blood mononuclear cells (PBMCs) will undergo further analysis and processing as detailed below.

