### Outcome measures

Our hypothesis is that patients with poor post-operative sublingual functional capillary density (defined as a PVD < 22 mm/mm^2 and MHI > 0.4) will have a higher degree of postoperative cardiovascular and pulmonary organ injury compared to patients with normal postoperative microcirculation. The primary outcome for this study will be VVFDs during the first 30 days after surgery. This outcome was chosen because our elective cardiac surgery patients are managed using early recovery after surgery (ERAS) protocols, with a goal to be extubated and weaned off vasopressors within 24 hours after surgery [21,22]. VVFDs will be calculated as a reverse count of consecutive days without requiring ICU-level respiratory or vasopressor support (**Error! Reference source not found.**). Our research group has used a similar primary outcome in a previous clinical trial [23]. The day of operation (day zero) will not be included as all patients undergoing cardiovascular surgery with CPB require mechanical ventilation and vasoactive medications on the day of surgery. Ventilator days will include mechanical ventilation via endotracheal tube or tracheostomy, high-flow nasal cannula  $\geq$  40 liters/minute with an FiO2 > 40%, or non-invasive positive pressure ventilation not prescribed at home. Non-invasive positive pressure ventilation and HFNC will be included as these both require the patient to remain in our ICU. Vasoactives include epinephrine, norepinephrine, vasopressin, phenylephrine, dobutamine, or milrinone at any dose. Subjects in need of respiratory or vasopressor support on day 30, or die before day 30 will be assigned zero VVFDs. If the patient is discharged prior to hospital day 30 a “last status carried forward” approach will be used. Secondary outcomes will include sequential organ failure assessment (SOFA) score on day 1, day 3, diagnosis of acute kidney injury (defined as an increase in serum creatinine  $\geq$  0.3 mg/dL within 2 days), and hospital length of stay.

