**Fig 3. Examples of VVFD scenarios to determine clinical outcomes.**

Exploratory outcomes will examine the relationship of microcirculatory function with common clinical biomarkers such as lactate,  $SvO_2$ , venous-to-arterial  $PCO_2$  gap, capillary refill time, and lactate to pyruvate ratio. Markers of endothelial injury and inflammation such as soluble vascular cell adhesion molecule 1 (sVCAM-1), soluble intercellular adhesion molecule 1 (sICAM-1), e-selectin, IL-8, IL-10, and other inflammatory cytokines will be measured. We will also examine mitochondrial complex function in human blood cells, comparing individual complex (I, II, III, and IV) function and reactive oxygen species generation between patients with and without post-operative shock.

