### Statistical and analysis plans

Continuous variables characterizing demographical data, microcirculation data, and mitochondrial respiration measurements, and outcomes data will be reported as means with standard deviations if normally distributed or medians with interquartile ranges if not normally distributed. Categorical variables will be represented as frequencies and proportions. To examine the predictive performance of selected variables for the primary outcome, we will construct receiver operator characteristic curves for threshold values of PVD, MHI, lactate,  $SvO_2$ , mean arterial pressure, and cardiac index. A Youden index will be calculated to determine the best cutoff value for determining prolonged VVFDs.

Linear regression modeling will be used to examine the relationship between L/P ratio and postoperative microcirculation variables. We will perform univariate analyses on candidate predictor variables of L/P ratio including PVD, MHI, LFTs, creatinine, CPB time, cross clamp time, and catecholamine administration. Multiple linear regression analysis will be used to model the effect of significant predictors. Repeated measure ANOVA will be used to compare changes in microcirculatory variables, mitochondrial respiration, and mitochondrial reactive oxygen species production over time. To adjust for multiple comparisons, post-hoc pairwise Tukey Kramer t-tests will be performed. All analyses will use statistical software (SAS version 15.1, Cary, NC; Prism v 9.0, Graph-Pad Software, San Diego, CA).

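### The lactate criterion for post-operative shock is written per decilitre, literally above 20 mmol/L; the sponsor should confirm the unit before the exploratory shock versus no-shock comparison (minor)

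*Combined protocol and SAP*

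**What the plan says.** Under Inclusion criteria, a patient is identified as being in shock after surgery when two conditions hold. The first is hypotension that needs a vasopressor, or a low output state treated with inotropes. The second is introduced as "Signs of end-organ injury or impaired tissue perfusion defined by one of the following criteria". Three alternatives follow:

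- capillary refill slower than 3 seconds in a normothermic patient;
- the lactate line, "Serum lactate $> 2$ mmol/dL";
- a mixed venous saturation below 60%.

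No other section defines shock in operational terms.

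The label is used in the exploratory paragraph that closes Outcome measures (after the Fig 3 caption). That paragraph plans to compare the function of individual mitochondrial complexes and "reactive oxygen species generation between patients with and without post-operative shock". Statistical and analysis plans names no test for this contrast. The mitochondrial analysis it does name is longitudinal: "Repeated measure ANOVA will be used to compare changes in microcirculatory variables, mitochondrial respiration, and mitochondrial reactive oxygen species production over time".

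**The concern.** A concentration per decilitre is ten times the same numeral per litre. Whoever codes the shock variable from this document has only this one line to follow for lactate. If the line is coded literally and the intended unit was per litre, the lactate route into the shock group becomes ten times more demanding than planned.

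The resulting error would run in one direction only: some patients the investigators meant to call shock would be placed in the no-shock group. What is at stake is the clean separation of the two groups in one exploratory comparison.

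**Working it through.** **1. Conversion.** Input: 2 mmol/dL (Inclusion criteria, item 2b). One litre is 10 dL, so 2 mmol/dL × 10 dL/L = 20 mmol/L. Ratio to the same numeral per litre: 20 / 2 = 10. The threshold is a definition and is not computed from anything else, so there is no plan calculation to reproduce.

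**2. Is there a second figure to check against?**

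- Introduction: mentions lactate and lactic acidosis, with no number or unit.
- Outcome measures, exploratory paragraph: names lactate and the lactate to pyruvate ratio, with no number or unit.
- Statistical and analysis plans: lists lactate for the ROC curves, where the cutoff is to be found from the data by the Youden index. No number or unit is given.
- Outcome measures, acute kidney injury: a creatinine rise of at least "0.3 mg/dL within 2 days". This is also per decilitre, but in mass units and for another analyte.

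The lactate line is the only use of a mmol unit in the documents, so they neither confirm nor contradict it.

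**3. Who would change group?** Take a patient who meets the first shock criterion.

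| Capillary refill or SvO2 qualifies | Lactate (mmol/L) | Label as written (> 20 mmol/L) | Label if per litre was meant (> 2 mmol/L) |
|---|---|---|---|
| Yes | any | shock | shock |
| No | up to 2 | no shock | no shock |
| No | above 2, up to 20 | **no shock** | **shock** |
| No | above 20 | shock | shock |

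Only the third row changes. Patients who do not meet the first criterion are no-shock under either reading.

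**4. Effect on the contrast.** Let f be the share of the labelled no-shock group that falls in the third row. Let Δ be the true mean difference between shock and no-shock. Assume that third-row patients have the same mean as the other shock patients. The expected observed difference is then Δ − fΔ = (1 − f)Δ, which is closer to zero. The documents give nothing from which f can be estimated.

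**5. What does not use the label.**

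- Eligibility: under Informed consent, patients are approached the day before surgery or in the preoperative area. Baseline measurements also precede surgery, so post-operative shock cannot be a condition of entry.
- Sample size: 134 subjects, with 140 to be enrolled. It rests on a 2-day difference in ventilator and vasopressor-free days between groups split at a PVD of 22 mm/mm², with a one-sided α of 0.05. Lactate and shock status do not enter.
- Primary outcome: it is counted from respiratory and vasoactive support and from death.

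**The case against.** The strongest reply is that this is a query about one character. No second figure conflicts with the line, so the documents do not prove it wrong, and the view that it is a slip is a presumption. Slips of single characters do occur elsewhere: perfused vessel density is abbreviated PWD in the video analysis section and the abbreviation list, but PVD in other places. The harm also needs a chain of conditions. A per-litre unit must have been intended, staff must nevertheless have applied 20 mmol/L, and a patient must qualify through lactate alone. The comparison must then be run, and it is exploratory with no named test. Lactate's other uses do not depend on this cutoff.

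All of that stands and keeps the point minor. It does not remove the point, because the line is a working decision rule in the only shock definition and checking it costs almost nothing.

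A reader might go further and infer that the lactate schedule is contradictory, or that lactate may not be on record. One section says "blood gas measurements will be collected upon ICU admission, then hourly during the first 6 hours", another says "Arterial blood gas samples will be obtained by clinical staff every 1-2 hours for the first 6 hours after ICU admission", and the named analytes end with "and glucose are also reported on each blood gas analysis". The documents do not support that inference. The first section describes study data collection and also covers perfusion data at the same times. The second describes draws made by clinical staff. The word also in the analyte sentence suggests additional items, not a complete list. The timing may be set out in Fig 1, which could not be seen here. None of this bears on the unit.

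**Conclusion.** The point holds as a minor one: a probable unit error, or at least an unclear definition. As written, the threshold is above 20 mmol/L, a factor of 10 from the same numeral per litre. The consequence depends on two assumptions that the documents cannot settle: that a per-litre unit was intended, and that the line is applied literally. If both hold, only third-row patients move, all from shock to no-shock, and only the exploratory mitochondrial comparison is touched.

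Two stronger conclusions might be drawn, and neither is supported. One is that patients have been misclassified; nothing shows how the criterion has been applied, and the number affected cannot be derived. The other is that the main result is at risk because the definition sits under Inclusion criteria. In use it classifies patients already enrolled, and the PVD groups, the primary outcome and the sample size do not depend on it.

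**What to change.** Before any shock versus no-shock comparison, the sponsor should:

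1. confirm the intended lactate unit and correct item 2b of Inclusion criteria if needed;
2. check that the case report form and the derived shock variable use that same unit;
3. re-derive the shock label only if the check finds a mismatch.

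Which threshold applies is for the sponsor to state; this review does not propose one. The cost is at most one unit edit and one check of the form and the variable code. Any re-derivation would draw on lactate values that the plan already needs for its ROC analysis. The sample size and the primary analysis stay as they are.
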